10.5.4 Binding Antibody Multiplex Assay

IgG antibodies binding to antigens (gp 145 Ref. Std.; 1086C_D7gp120.avi/293F, Con S gp140 CFI, Con 6 g120/B, gp41, 1086C_V1_V2 Tags) will be measured using binding Ab multiplex assay (BAMA) as the primary analysis. Contingent on the primary analysis results of antigens listed above, a secondary set of IgG clone; H2 may be assessed. For the primary analysis, BAMA will be assayed for all samples at three time points (visits 2, 4 and 9). Specimens collected at visits 6 and/or 11 may also be assayed base on the results on the initial assay.

Serum HIV-1 specific IgG responses against these antigens are measured on a Bio-Plex instrument (Bio-Rad). The Bioplex software provides 2 readouts: a background-subtracted mean fluorescent intensity (MFI), where background refers to a plate level control (i.e., a blank well run on each plate), and a concentration based on a standard curve, if provided. Samples from post-enrollment visits are declared to have positive responses if they meet three conditions: (1) based on the 95th percentile of the baseline visit serum samples and at least 100 MFI), (2) the MFI minus Neg values are greater than 3 times the baseline (visit 2) MFI minus Neg values, and (3) the MFI values are greater than 3 times the baseline MFI values. Background-adjusted MFI is used to summarize the magnitude at a given time-point. If sufficient immunogenicity is observed, samples may be titrated to calculate antibody titrations. Titrations are quantified by EC50/AUC.

The following analysis will be performed for each tested antigen separately. Positive response rates will be compared between treatment groups using the Barnard's exact test. Response magnitudes will be compared between treatment groups using the Wilcoxon rank sum test. Positive response rates will be compared within treatment group, across timepoints using the McNemar's test. Response magnitudes will be compared within treatment group, across timepoints using the Wilcoxon signed rank test. All p-values are two-sided. False-discovery-rate adjusted q-values [8] will be calculated to account for multiple antigens for each type of comparisons. Statistical significance is claimed if the unadjusted p-value is < 0.05 and the adjusted p-value (q-value) is < 0.2 .

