12.2.1 List of Tables

- Response rate table by lab, isotype, antigen, visit, day, and group/treatment arm
- Listing of magnitudes (MFI*) among positive responders.
- Summary statistics (i.e., min, mean, median, max) among responders by lab, isotype, antigen, visit, day, and group/treatment arm.
- Summary statistics (i.e., min, mean, median, max) among all participants (positive and negative responders) by lab, isotype, antigen, visit, day, and group/treatment arm.
- Comparisons of response rates between treatment groups at each visit.
- Comparisons of response magnitudes among responders between treatment groups at each visit, if there are at least 5 responders within each group at a given visit.
- Comparisons of response rates between visits 4 and 9 for each treatment group.

- Comparisons of response magnitudes among responders between visits 4 and 9 for each treatment group if there are at least 5 responders at each visit within a given treatment group.

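### The between-dose BAMA magnitude test leaves out each participant's visit 2 reading; an added all-participant, baseline-adjusted comparison would gain power only if visit 2 predicts the later reading

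*SAP*

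**What the plan says.** SAP 10.5.4 (Binding Antibody Multiplex Assay) sets out the measurement and the test.

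- Timing: "BAMA will be assayed for all samples at three time points (visits 2, 4 and 9").
- Magnitude: "Background-adjusted MFI is used to summarize the magnitude at a given time-point". The correction is for the plate, not the person: "background refers to a plate level control (i.e., a blank well run on each plate").
- Between-group test: "Response magnitudes will be compared between treatment groups using the Wilcoxon rank sum test". No covariate, change score or ratio to visit 2 is named, and the general approach in SAP 10.5.1 names none.
- Use of visit 2: it enters the positivity call. One condition is that "the MFI minus Neg values are greater than 3 times the baseline (visit 2) MFI minus Neg values"; another applies the same threefold rule to the MFI itself; the remaining one uses the 95th percentile of baseline sera with a floor of 100 MFI.
- Decision rule: "All p-values are two-sided", and "Statistical significance is claimed if the unadjusted p-value is < 0.05" together with a q-value below 0.2.

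SAP 12.2.1 narrows the comparison that will be tabulated: "Comparisons of response magnitudes among responders between treatment groups at each visit", provided each group has at least 5 responders. Section 10.5.4 does not mention this restriction.

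**The concern.** Levels of binding antibody after one and after three injections are secondary endpoints (protocol 5.2), and the SAP tests them between groups in small arms. A pre-vaccination reading on the same antigen exists for everyone. If it predicts the later reading, part of the spread within each arm can be explained and removed at no assay cost. The threefold rules show that the SAP allows for pre-vaccination reactivity to differ between people, but the magnitude test does not use that difference.

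The gain could matter most at visit 4. After a single injection the induced signal is likely to be smallest relative to any reactivity already present. What is at stake is precision in a secondary comparison, not its validity.

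**Working it through.** **Inputs.** From the documents: 25 and 15 randomized to the two doses (protocol 6.1), 10% missing immunogenicity data (protocol 6.1.2), two-sided 0.05 (SAP 10.5.4). Assumed, because the documents give neither: the correlation ρ between visit 2 and the later reading, and the size of the dose shift in SD units.

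**The plan's own figures.** No power is stated for magnitudes. The nearest figures are the evaluable numbers and Table 6-3. 0.9 × 25 = 22.5 and 0.9 × 15 = 13.5, rounded down to 22 and 13. The score interval for 11/22 is 0.5 ± 1.96 × √(0.25/22 + 3.84/(4 × 22²)) / (1 + 3.84/22) = 0.5 ± 0.193, or 30.7% to 69.3%, as printed. All 21 rows of the table agree within 0.1 point.

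**What adjustment can do.** Adjusting for baseline multiplies the residual SD by √(1 − ρ²). The standard error factor is √(1/22 + 1/13) = 0.350. The difference detectable with 80% power is therefore (1.960 + 0.842) × 0.350 × √(1 − ρ²) = 0.98 × √(1 − ρ²) SD.

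**Simulation.** 5,000 trials per row, bivariate normal, 22 v 13, all participants, true shift 0.8 SD. The Wilcoxon rank sum is compared with a rank analysis of covariance on visit 2.

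| ρ | √(1 − ρ²) | Detectable difference (SD) | Wilcoxon power | Adjusted power | Difference (points) |
|---|---|---|---|---|---|
| 0 | 1.000 | 0.98 | 57.5% | 57.1% | −0.4 |
| 0.1 | 0.995 | 0.975 | 57.6% | 56.8% | −0.8 |
| 0.2 | 0.980 | 0.96 | 57.6% | 58.1% | +0.5 |
| 0.3 | 0.954 | 0.935 | 57.2% | 59.4% | +2.2 |
| 0.5 | 0.866 | 0.849 | 57.1% | 67.6% | +10.5 |
| 0.7 | 0.714 | 0.700 | 58.0% | 82.6% | +24.6 |

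Each power carries a Monte Carlo standard error of about √(0.57 × 0.43/5000) = 0.7 point. Type I error of the adjusted test was 4.5% to 5.5%. A separate set of 4,000 trials per scenario gave 60% v 59% at ρ = 0, 59% v 61% at 0.3, 58% v 68% at 0.5 and 57% v 81% at 0.7. With a 1 SD shift the pattern is the same: 78.1% v 77.3% at 0, 77.4% v 80.1% at 0.3, 75.6% v 85.5% at 0.5. All of these use p < 0.05 alone and ignore the added q-value condition.

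**A less favourable model.** Let the later reading be baseline plus an independent induced signal, with assumed log10 SDs of 0.4 and 0.5, median baseline 20 to 200 MFI and median induced signal 200 to 10,000 MFI. In most settings the rank correlation is then 0.00 to 0.17 and the two tests agree within about 1 point. A clear gain appears only when baseline is as large as the induced signal (200 v 200 MFI: 37% to 45%; a repeat gave 39% to 47%). At 100 v 200 MFI it is 47% to 50%.

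**Within responders.** In those last two settings, restricting to responders by the threefold rule and then adjusting lowered power: 23% to 19% and 16% to 12%, with 21% to 18% and 18% to 14% in a repeat. Selecting on the ratio to visit 2 itself creates correlation between visit 2 and the later reading. The size of the loss depends on how the positivity rule is modelled. When the 95th-percentile condition was modelled as well, a check showed neither loss nor gain.

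**Change from visit 2.** With equal SDs its variance factor is 2(1 − ρ), which exceeds 1 when ρ < 0.5. At a 1 SD shift, normal-approximation power falls from 81.6% to 52.4% at ρ = 0 and draws level only at ρ = 0.5.

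**The case against.** The strongest reply is that visit 2 is already used where the SAP needs it. It decides who is a responder, and only responders enter the listed magnitude test. A responder's baseline is below one third of the later reading, so subtracting it leaves more than two thirds and moves the log10 value by less than log10(1.5) = 0.18. This stands for responders, and it rules out saying that the plan ignores visit 2. It does not cover non-responders, for whom baseline may be a large part of the reading.

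Second, the benefit rests on a correlation that nobody has shown. Participants are HIV-seronegative and recipients of earlier HIV vaccines are excluded (protocol 7 and 7.2), so visit 2 may be mostly assay background. A threefold-rise rule guards against false positives; it is not evidence that baseline predicts the later level. This stands too, and it is why the gain has to be stated as a range that includes a small loss.

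Third, the 22 v 13 figures describe all evaluable participants, not the responder comparison the SAP lists. That is correct. The remedy therefore changes the analysis set as well as the test, and should say so. The change has its own reason: responder status arises after randomization, so only the all-participant comparison keeps randomization's protection. SAP 12.3.1 already lists neutralizing titer comparisons both among responders and among all participants.

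Finally, protocol 6.1.2 aims at preliminary estimation of response rates and claims no power for magnitudes. That limits the priority of the point.

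**Conclusion.** The point holds as a low-priority, conditional matter of efficiency. Visit 2 is measured in everyone, and the between-dose magnitude test does not adjust for it. In all participants at 22 v 13 with an assumed 0.8 SD shift, adjustment costs about 1 point of power at zero correlation, makes no material difference up to about 0.2, and gains about 2 to 3 points at 0.3, 10 at 0.5 and 24 at 0.7. Which of these applies cannot be told from the documents and may differ by antigen and visit.

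A reader might infer that the planned comparison is biased or invalid for want of baseline adjustment. It is not: dose is randomized, and omitting a baseline covariate does not bias the comparison. The restriction to responders is a separate matter. A reader might also infer that removable noise is known to remain, or that the Wilcoxon should be replaced. The documents support neither, because they give no correlation and the Wilcoxon is a valid test.

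**What to change.** In SAP 10.5.4 and 12.2.1, add a prespecified comparison of Group 1 v Group 2 at visits 4 and 9, for each antigen, in all participants with data rather than responders only. Use rank analysis of covariance, with the visit 2 background-adjusted MFI for the same antigen as covariate. Keep the planned Wilcoxon alongside it, and state in 10.5.4 the responder restriction that 12.2.1 imposes on it. Report the correlation of visit 2 with visits 4 and 9 per antigen, so that the reader can see whether adjustment had anything to work with.

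Do not apply the adjustment inside the responder subset, which is defined from visit 2, and do not substitute a change from visit 2.

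The cost is SAP wording, a few lines of code, one more analysis per antigen and visit, and about 1 point of power in the adjusted test if the correlation is near zero. No new sample or assay is needed.

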10.5.5 Neutralizing Antibody

Neutralizing antibodies against HIV-1 will be measured as a function of reductions in Tat-regulated luciferase (Luc) reporter gene expression in TZM-bl cells. Neutralization ID50 titers will be measured against Env vaccine strain (6980.v0.c22) and a single highly neutralization-sensitive Tier 1 virus as a positive control (MW965.26) for all available visit 9 samples. The global panel and/or clade-specific panels will be used to assess Tier 2 neutralization [6,7] initially in a subset of 15 participants randomly selected from Groups 1-3, and may expand to the remaining samples. Assays will be performed on specimens obtained at 2 weeks post 3th vaccination (visit 9) to assess the protocol secondary objective 3. Additional assays may be performed on the first day of vaccination (visit 2, baseline), 2 weeks post 1st vaccination (visit 4), 2 weeks post 2nd vaccination (visit 6), and 6 months post 3rd vaccination (visit 11, durability timepoint) for exploratory analyses.

A response is considered positive if the neutralization titer ID50 is above 10. . Magnitude of response will be measured by the natural log of the ID50 titer. An aggregate measure of response against the global panel will be calculated as the area-under-the-magnitude-breadth curve (AUC-MB), which is equivalent to the mean log titer across all viruses in the panel. If a titer is left censored, half the left censor limit will be used as the titer value.

Positive response rates are compared between treatment groups using the Barnard's exact test. Response magnitudes and AUC-MBs are compared between treatment groups using the Wilcoxon rank sum test. If data are available from multiple time-points, positive response rates are compared within treatment group, across timepoints using the McNemar's test and response magnitudes using the Wilcoxon signed rank test. Statistical tests with a p-value ≤ 0.05 will be considered statistically significant.

11 SAFETY TABLES, PARTICIPANT LISTINGS, AND FIGURES

11.1 List of Tables

The following tables are included in the SMB reports and FSR for Safety:

- Enrollment Report
- Demographics and Vaccination Frequencies
- Overall Protocol Status
- Maximum Local and Systemic Reactogenicity Summaries
- Adverse Experiences by Body System and Severity – By Decreasing Frequency
- Adverse Experiences by Preferred Term and Severity – By Decreasing Frequency – Includes Severe, Life-threatening or Fatal Experiences Only
- Adverse Experiences by Preferred Term and Severity – By Decreasing Frequency – Includes Experiences of All Severities
- Adverse Experiences by Preferred Term and Relationship to Study Product – By Decreasing Frequency – Includes Related Experiences Only
- Adverse Experiences by Preferred Term and Relationship to Study Product – By Decreasing Frequency – Includes Experiences of Any Relationship
- Expedited Adverse Experiences (EAEs) Reported to the Regulatory Support Center (RSC)
- Pregnancy Listing

11.2 List of Participant Listings

These participant listings are included in the SMB reports:

- Discontinuation Status
- Pregnancies
- Severe or Life-Threatening Local and Systemic Reactogenicities
- Moderate or Severe Erythema and Induration
- Expedited Adverse Experiences (EAEs)
- Severe, Life-Threatening, or Fatal Adverse Experiences
- Adverse Experiences with Relationship to Study Product
- HIV Infection Results from Lab and Reported by Site
- Study Product Administration Error

11.3 List of Figures

These graphs are included in the SMB reports and FSR for Safety:

- Maximum Local Reactogenicities
- Maximum Systemic Reactogenicities
- Boxplots for WBC, neutrophils, lymphocytes, hemoglobin, platelets, ALT, and creatinine

12 IMMUNOGENICITY TABLES AND FIGURES, BY ASSAY

12.1 Intracellular Cytokine Staining

Cellular immune responses will be measured by ICS using the following synthetic peptide pools: Env-1-PTEG-SEQ, Env-2-PTEG-SEQ, Env-3A-PTEG-SEQ, Env-3B-PTEG-SEQ. The following functional markers will be measured from a 17-colorimetric panel: CD4 BUV39, CD3 BUV737, IFN- γ V450, AViD, CD14 BV510, CD56 BV570, PD-1 (CD279) BV605, CD8 BV650, ICOS (CD278) BV711, CCR7 BV786, TNF- α FITC, IL-4 PerCP-Cy5.5, IL-2 PE, CXCR5 PE-Dazzle594, IL-17a PE-Cy7, CD154 APC, Granzyme B Alx700, CD45RA APC-H7.

ICS will be performed on specimens from all participants collected at 2 weeks post 3rd vaccination (visit 9) to assess the protocol secondary objective 3. Additional assays may also be performed on specimens collected at 2 weeks post 1st vaccination (visit 4), at 2 weeks post 2nd vaccination (visit 6) at 6 months post 3rd vaccination (visit 11, durability/memory timepoint) for exploratory analyses.

12.1.1 List of Tables

- Response rate table by lab, T-cell subset, peptide pool, visit, day, and group/treatment arm for cells expressing either IL-2 and/or IFN- γ using Fisher's exact test criteria.
- Listing of positive responders for cells expressing either IL-2 and/or IFN- γ .
- Summary statistics (i.e., min, mean, median, max) among responders for T-cell subset, peptide pool, visit, and group/treatment arm

- Summary statistics (i.e., min, mean, median, max) among all participants (positive and negative responders) for T-cell subset, peptide pool, visit, and group/treatment arm.
- Response rate and/or response magnitude comparison of treatment arms.

12.1.2 List of Graphs

- Boxplots of background-adjusted IFN- γ and/or IL-2 response magnitude by T-cell subset, HIV protein, visit, and group/treatment arm using the Fisher exact test.
- Boxplots of background-adjusted marginal functional marker response magnitude by T-cell subsets, HIV genes, visits, and groups if requested. The default layout of boxplots will be with all available time points by treatment group on the same graph, one T-cell subset per graph.
- Boxplots of cytokine degree by T-cell subset, HIV protein, visit, and group/treatment arm if polyfunctional graphs are requested. The default layout of boxplots will be with all available time points by treatment group on the same graph, one T-cell subset per graph.
- Boxplots for each cytokine combination of a given degree by T-cell subset, HIV protein, visit, and group/treatment arm if polyfunctional graphs are requested. The default layout of boxplots will be with all available time points by treatment group on the same graph, one T-cell subset per graph.
- If assays are run for visit 4, visit 6 and/or 11, spaghetti plots will be produced to show IFN- γ and/or IL-2 response magnitude over time, with one graph per T-cell subset and HIV gene, with separate panels for treatment groups. The default layout of boxplots will be with all available time points by treatment group on the same graph, one T-cell subset per graph.

12.2 Binding Antibody Multiplex Assay

IgG antibodies binding to antigens (gp 145 Ref. Std.; 1086C_D7gp120.avi/293F, Con S gp140 CFI, Con 6 g120/B, gp41, 1086C_V1_V2 Tags) will be measured using binding Ab multiplex assay (BAMA) as the primary analysis. Contingent on the primary analysis results of antigens listed above, a secondary set of IgG clone; H2 may be assessed. For the primary analysis, BAMA will be assayed for all samples at three time points (visits 2, 4 and 9). Specimens collected at visits 6 and/or 11 may also be assayed base on the results on the initial assay.

12.2.1 List of Tables

- Response rate table by lab, isotype, antigen, visit, day, and group/treatment arm
- Listing of magnitudes (MFI*) among positive responders.
- Summary statistics (i.e., min, mean, median, max) among responders by lab, isotype, antigen, visit, day, and group/treatment arm.
- Summary statistics (i.e., min, mean, median, max) among all participants (positive and negative responders) by lab, isotype, antigen, visit, day, and group/treatment arm.
- Comparisons of response rates between treatment groups at each visit.
- Comparisons of response magnitudes among responders between treatment groups at each visit, if there are at least 5 responders within each group at a given visit.
- Comparisons of response rates between visits 4 and 9 for each treatment group.

- Comparisons of response magnitudes among responders between visits 4 and 9 for each treatment group if there are at least 5 responders at each visit within a given treatment group.

12.2.2 List of Graphs

- Barplots of response rates by isotype, antigen, visit day, and group/treatment arm.
- Spaghetti plot of background-adjusted MFI over time by antigen, antibody class (if applicable), visit, sample type and group, with boxplots among responders overlaid.

12.3 Neutralizing Antibody

Neutralization ID50 titers will be measured against Env vaccine strain (6980.v0.c22) and a single highly neutralization-sensitive Tier 1 virus as a positive control (MW965.26). The global panel of 9 viruses: 246F3, Ce1176, CNE55, X1632, Ce0217, BJOX2000, 25710, TRO11, CH119 are used to assess Tier 2 neutralization [6,7]. Assays will be performed on specimens obtained at 2 weeks post 3th vaccination (visit 9) to assess the protocol secondary objective 3. Additional assays may be performed on the first day of vaccination (visit 2, baseline), 2 weeks post 1st vaccination (visit 4), 2 weeks post 2nd vaccination (visit 6), and 6 months post 3rd vaccination (visit 11, durability timepoint) for exploratory analyses.

12.3.1 List of Tables

- Response rate table by lab, virus tier, virus, visit, and group/treatment arm.
- Listing of positive responders based on the criteria used for the response rate table(s).
- Summary statistics (i.e., min, geometric mean, median, max) of ID50 titers among responders by lab, virus tier, virus, visit, and group/treatment arm
- Summary statistics (i.e., min, geometric mean, median, max) of ID50 titers among all participants (positive and negative responders) by lab, virus tier, virus, visit, and group/treatment arm
- Comparisons of response rates between Group 1 vs. Group 3, Group 2 vs. Group 3, and Group 1 vs. Group 2 for each of the non-global panel viruses
- Comparisons of ID50 titers between Group 1 vs. Group 2 for each of the non-global panel viruses among responders.
- Comparisons of ID50 titers between Group 1 vs. Group 2 for each of the non-global panel viruses among all participants, with the titer of non-responders censored at 5.
- Comparison of AUC-MB between Group 1 vs. Group 2.

12.3.2 List of Graphs

- Boxplots of neutralizing antibody titers by virus, and group/treatment arm for the non-global panel viruses
- Boxplots of neutralizing antibody titers by virus and group/treatment arm for the global panel viruses
- If assays are run for visits 2, 4, 6 and/or 11, spaghetti plots of neutralizing antibody titer over time by cell type, isolate and group

- Magnitude-breadth (M-B) plots of titer and breadth for the global panel of 9 viruses by group/treatment arm.

